8 TRIAL ASSESSMENT OF SAFETY

8.1 Adverse Events

Adverse events (AEs) are defined as any unfavorable or unintended change in the physical, psychological, or biochemical condition of the subject. An AE temporally related to participation in the trial or due to a procedure performed in the trial, will be documented whether or not considered related to the test article. This definition includes intercurrent illnesses and injuries, and exacerbations of pre-existing conditions. Stable pre-existing conditions which do not change in nature or severity during the trial are not considered AEs; however, these should be collected as part of the medical history. AEs will be considered treatment emergent from the date and time of the first administration of the investigational product.

Data concerning all classes of adverse events will be collected at scheduled visits from the time informed consent is obtained on Day 0 through Day 28, inclusive. After these specified days, data concerning MAEs, SNMCs, and SAEs will be collected (see Sections 8.1.4 and 8.2 for details of these AEs), as well as additional information regarding outcomes/resolutions of AEs reported prior that had no stop date recorded. In addition to the scheduled visits, subjects will be instructed to notify the investigator and/or return to the clinic if any severe AE (solicited or otherwise) or event fulfilling the definition of an SAE occurs at any time following vaccination. If at a scheduled or unscheduled visit, symptoms are presented that would require a physical exam to adequately assess potential AEs, the exam should be performed and vital signs collected. Adverse events will be recorded as observed by the investigator, designated personnel, or as provided by the subject on the diary card or during the in-person visit. Full details of the AE (ie, nature, date of onset, and recovery, as well as an assessment of severity, relationship to trial treatment [unsolicited events only], seriousness, treatment, and outcome) will be recorded in the source documentation and captured in the eCRF, and will generally require the investigator(s) causality assessment, except as discussed below.

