6.2 Concomitant Medication

The assessment of concomitant medication use by the subject during the study will coincide with the collection period of adverse events. Concomitant medications recorded on the Concomitant Medications CRF will be summarized by WHO-DRUG Anatomical Therapeutic Chemical (ATC) Term and standardized (generic) medication name based on WHODD GLOBAL B3-Mar2019. The number (percentage) of subjects who record one or more concomitant medications will be presented by treatment group for all subjects in the Safety Population. Multiple occurrences of medication usage for a subject will be counted only once within an ATC term and standardized medication name. The presentation of concomitant medications will include all medications recorded on the Concomitant Medications CRF, including medications with a missing or partial start date or a start date prior to Study Day 0 vaccination. A separate listing of treatment-emergent new concomitant medications will be presented.

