12.5 Missing, Unused, and Spurious Data

In general, there will be no substitutions made to accommodate missing data points. All data recorded on the eCRF will be included in data listings that will accompany the CSR.

When tabulating AE, Concomitant Medications, and Hospitalizations data, partial dates of event onset will be handled as follows:

- If the day of the month is missing, the onset date will be assumed to be the date of the Day 0 vaccination or first of the month, whichever is later, in order to conservatively report the event as vaccine-emergent.
- If the month or year (or both) of the onset date is missing, impute month or year (or both) which makes the imputed date most adjacent to the first dosing date.
- If the onset day and month are both missing, the event onset will be coded to the date of the Day 0 vaccination or 1st January of the year, whichever is later, in order to conservatively report the event as vaccine-emergent.
- A completely missing onset date will be coded as the date of the Day 0 vaccination, unless the end date suggests it could have started prior to this in which case impute the 1st January of the same year as the end date.
- When imputing a start date ensure that the new imputed date is prior to the end date of the AE or med.

A conservative approach will be taken to assess the relationship of an event to test article: if the relationship of an event is missing, it will be considered treatment-related. Missing severity for an AE will not be imputed.

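### SAP 12.5: requiring an imputed start before the end date conflicts with imputing Day 0 for records ending that day, and the wholly-missing-onset exception has an undefined trigger

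*SAP*

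**What the plan says.** SAP 12.5 opens with "When tabulating AE, Concomitant Medications, and Hospitalizations data, partial dates of event onset will be handled as follows" and gives five bullets.

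- **Bullet 1 (day missing) and bullet 3 (day and month missing):** take the later of the Day 0 date and the first of the known month or year, "in order to conservatively report the event as vaccine-emergent".
- **Bullet 2 (month or year missing):** choose the value that brings the date closest to dosing.
- **Bullet 4 (nothing known):** "A completely missing onset date will be coded as the date of the Day 0 vaccination". The exception to this default reads "unless the end date suggests it could have started prior to this in which case impute the 1st January of the same year as" that in which the record ends.
- **Bullet 5 (ordering check):** "When imputing a start date ensure that the new imputed date is prior to the end date of the AE or med".

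These dates are used in several places. SAP 8.1.2 tabulates unsolicited events over Days 0–28 and again over Days 0–364. SAP 6.2 summarises all medications, "including medications with a missing or partial start date or a start date prior to Study Day 0 vaccination", and adds: "A separate listing of treatment-emergent new concomitant medications will be presented". Protocol 8.1 collects all classes of adverse event "from the time informed consent is obtained on Day 0 through Day 28, inclusive", and counts an event as treatment-emergent from the date and time of administration.

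**The concern.** Two things in these bullets do not fit together.

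1. **Ordering check.** Bullets 1, 3 and 4 can each produce the Day 0 date. Bullet 5 rejects that date whenever the record also ends on Day 0. The only dates left are before vaccination.
2. **Exception in bullet 4.** The plan does not say what makes an end date suggest an earlier start, and nothing requires the imputed 1 January to fall before Day 0. The trial vaccinates for the 2019–20 season and follows subjects for about a year, so some end dates will fall in the calendar year after vaccination.

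At stake is whether a few poorly dated records land inside or outside the Days 0–28 safety tables, and which drugs appear as new in the medication listing. Two programmers could date the same record differently and both claim to follow the SAP.

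**Working it through.** The plan gives no figure to reproduce; the check is calendar arithmetic. The rules come from SAP 12.5. Neither document states enrolment dates, so Day 0 is an assumption: 3 September 2019 (the date of protocol version 3.0, given in the SAP change history) to 31 December 2019, with 15 October 2019 for the examples.

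**Fault 1: the ordering check.** Take Day 0 = 15 October 2019.

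| Known onset | End date | Imputed by bullets 1, 3 or 4 | Latest date bullet 5 allows |
|---|---|---|---|
| none | 15 Oct 2019 | 15 Oct (bullet 4) | 14 Oct, Day −1 |
| October 2019 | 15 Oct 2019 | later of 15 Oct and 1 Oct = 15 Oct (bullet 1) | 14 Oct, Day −1 |
| 2019 | 15 Oct 2019 | later of 15 Oct and 1 Jan = 15 Oct (bullet 3) | 14 Oct, Day −1 |
| November 2019 | 1 Nov 2019 | later of 15 Oct and 1 Nov = 1 Nov (bullet 1) | 31 Oct, contradicting the recorded month |

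The first three rows lose vaccine-emergent status. The fourth stays post-vaccination but leaves its known month. If the start may equal the end date, all four imputed dates stand. The check itself is needed: it stops a record that ended before Day 0 from being given a Day 0 start. Only its strictness is at fault. This fault does not depend on how bullet 4's trigger is read.

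**Fault 2: the exception.** Write D for Day 0, E for the end date and J(E) for 1 January of the year of E. J(E) ≤ E always.

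- If E < D, then J(E) ≤ E < D. The record is pre-vaccination, as intended.
- If E ≥ D in the same calendar year, then J(E) ≤ D. The record is moved before vaccination (unless D is itself 1 January).
- If E falls in a later calendar year than D, then J(E) > D. A record supposed to have started before vaccination is dated after it.

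With D = 15 October 2019 and onset wholly missing:

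| End date | Narrow trigger (E < D) | Wide trigger (any end date compatible with an earlier start) |
|---|---|---|
| 14 Oct 2019 | 1 Jan 2019, Day −287 | 1 Jan 2019, Day −287 |
| 17 Oct 2019 | Day 0 | 1 Jan 2019, Day −287 |
| 20 Dec 2019 | Day 0 | 1 Jan 2019, Day −287 |
| 10 Jan 2020 | Day 0 | 1 Jan 2020, Day 78 |
| 1 Mar 2020 | Day 0 | 1 Jan 2020, Day 78 |

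Days from Day 0 to 1 January 2020: 120 for 3 September (27 + 31 + 30 + 31 + 1), 92 for 1 October, 78 for 15 October, 61 for 1 November, 32 for 30 November and 1 for 31 December. Since 4 December plus 28 days is 1 January, the wide reading puts the onset after Day 28 for any Day 0 up to 3 December 2019.

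**The case against.** **The exception has a sensible reading.** The default for a wholly missing onset is Day 0. If the trigger means an end date before Day 0, the exception never lands after vaccination. The wide reading would take in nearly every record with an end date and leave the default almost unused. This largely stands. A reader might infer that every record ending in 2020 is dated two to three months after vaccination, so that the rule does the opposite of what it intends. The documents do not support that: a 2020 end date alone does not invoke the exception, and the two to three months needs enrolment dates that are not given. What remains is that the text does not settle the reading. An end date before Day 0 proves an earlier start; the words chosen ask only whether one was possible. Also, adverse events are collected from consent on Day 0, so one could end before vaccination only if the injection was deferred (up to 7 days for acute illness, Protocol 6.1.1). The narrow reading therefore leaves the exception nearly empty for adverse events, though it remains useful for medications.

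**The conservative aim is not stated in bullet 4.** This is correct; it stands in bullets 1 and 3. Fault 2 should not be described as reversing bullet 4's declared purpose. On the wide reading, an event dated 1 January 2020 is also still post-vaccination and stays in the Days 0–364 tables.

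**Few records can be affected.** Date of onset is a required detail (Protocol 8.1), queries are resolved before analysis (Protocol 9.2), and subjects are watched for 30 to 60 minutes after injection and then keep a diary. A same-day reaction with a known end date and an incomplete onset will be rare, and a programmer may well take bullet 5 to mean no later than the end date. All of this limits the size, but it does not remove the contradiction in the wording.

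**Conclusion.** Two wording faults hold, both minor.

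- **Ordering check.** Bullet 5 contradicts bullets 1, 3 and 4 for any record ending on the date those bullets impute. When that date is Day 0, the literal result is a pre-vaccination onset, contrary to the aim stated in bullets 1 and 3.
- **Exception.** Bullet 4 works on the narrow reading. On the wide reading it misdates in both directions: 1 to 120 days after Day 0 for records ending in 2020, and before vaccination for records ending after Day 0 in 2019. The range rests on the assumed Day 0 dates.

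The documents do not give the number of records with incomplete onset; it is probably very small. The effect is confined to adverse event, medication and hospitalization tabulations and listings.

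**What to change.** Make two changes in SAP 12.5.

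1. In bullet 5, let the imputed start be *on or before* the end date.
2. In bullet 4, restate the exception as: *unless the end date is before the Day 0 vaccination, in which case the record is classed as pre-vaccination*.

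The cost is two sentences and the matching date-derivation code. The downside is that some pre-existing conditions and long-standing drugs with no start date will be dated to Day 0 and count as vaccine-emergent. The change therefore does not keep such drugs out of the listing of new medications in SAP 6.2. It makes their handling explicit and the same for every record.

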APPENDIX 1 – QNIV-E-301 TRIAL PROCEDURES SCHEDULE

Trial Day:	0	3	7	28	90	182	364
Window (days):		± 1	± 1	± 4	± 7	± 7	± 14
Trial Procedures							
Trial Informed Consent	X						
Inclusion/Exclusion Criteria	X						
Medical/Medication History	X						
Physical Exam	X		X [4]	X [4]		X [4]	
Vital Signs	X [1]		X	X		X	
Serology	X			X		X	
PMBC for CMI	$X^{[5]}$		X ^[5]	$X^{[5]}$		$X^{[5]}$	
Trial Treatment Injection	X						
Adverse Event Review [2]	X	X	X	X	X	X	X
Concomitant Medications Review [2]	X	X	X	X	X	X	X
Subject Diary Review				X [3]			
End of Trial							X

Note: Procedures shaded in grey are performed via scripted telephone call.

^[1] Vital signs to be captured pre-vaccination and between 30 to 60 minutes post-vaccination.

^[2] All adverse events and concomitant medications taken will be collected through Day 28; thereafter, only MAEs, SAEs, and SNMCs and medications taken for these events will be collected.

[figure not shown]
^[3] The subject diary will be reviewed by the investigator and collected at the Day 28 visit.

^[4] If needed, a physical examination may be performed, based on the investigator's discretion.

^[5] To be collected from a subset of approximately 140 subjects from several pre-designated clinical sites.

APPENDIX 2 – QNIV-E-301 SUBJECT MEASUREMENT TOOL

(Do not use this page in clinic, as it may not be to exact scale)

The Subject Measurement Tool consists of a transparent set of concentric circles with diameters that correspond to the ranges in the toxicity grading scale (2.5, 5, and 10 cm, in diameter). Subjects are instructed to overlay the template over the injection site for any reaction that can be visually observed (eg, redness, swelling, bruising). An assessment of severity is then made by determining the circle that best describes the size of the reaction: reactions that are smaller than Circle A (2.5 cm) are considered Grade 0; reactions larger than Circle A but equal to or smaller than Circle B (5 cm) are considered Grade 1; reactions larger than Circle B but equal to or smaller than Circle C (10 cm) are considered Grade 2; reactions larger than Circle C are considered Grade 3. The table below summarizes the severity grading for visible injection site reactions based on size.

Definition of Severity Grading for Visible Local Adverse Events

	•	
Severity Grade	Injection Site Grading Description	
0 - Normal	Reaction size fits inside Circle A	
1 - Mild	Reaction size larger than Circle A, but fits inside Circle B	
2 - Moderate	Reaction size larger than Circle B, but fits inside Circle C	
3 - Severe	Reaction size larger than Circle C
